2.2.2. Important Risks

2.2.2.1. Identified and Potential Risks of RMC-4630

RMC-4630 is currently being evaluated as monotherapy and in multiple combination studies. The Phase 1, first-in-human study in adult subjects with relapsed/refractory solid tumors (NCT03634982) has established a RP2DS of [REDACTED] of each week in a 21-day cycle. The toxicity profile of RMC-4630 in humans is emerging and is provided in detail in the current RMC-4630 IB. Dose modification guidance for selected toxicities is provided in Section 6.7 and supportive care guidelines are provided in Section 6.7.1.

are summarized below.

of subjects in study RMC-4630-01.

The median time to

first onset of a

As of 17-Jul-2022, a total of [REDACTED] across the clinical development program had a reported event (irrespective of attribution to study drug(s)) consistent with [REDACTED] which include [REDACTED] with an [REDACTED] and 1 subject with an event of interstitial lung disease. Of the [REDACTED] with an event, 1 [REDACTED] received RMC-4630 monotherapy, while the remaining [REDACTED] received RMC-4630 in combination therapy (4 subjects with cobimetinib, 2 subjects with osimertinib, and 2 subjects with pembrolizumab). A total of 7 subjects had an event which was [REDACTED] which included [REDACTED] with a [REDACTED] (1 subject who received RMC-4630 with cobimetinib and 1 subject who received RMC-4630 with osimertinib).

In addition to the risks described above, thromboembolic events are being monitored. As of

for subjects with

Because full cytochrome P-450 (CYP) isoform phenotyping studies for RMC-4630 have not been completed, RMC-4630 remains a putative substrate of CYP3A4; precautions should be taken with co-administration of strong CYP3A4 inducers or inhibitors. These agents are contraindicated in this trial (see [Appendix 8](#)).

Based on published on-target effects from other small-molecule inhibitors of the RAS signaling pathway, including inhibitors of RTKs, and/or nonclinical toxicology studies with RMC-4630, the following toxicities (listed alphabetically) are possible:

[REDACTED] . In general, toxicities are dose dependent and, in the case of MEK inhibitors, may also increase in frequency and severity with dosing duration.

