2.2.2.4. Steps to Minimize Risk

The RMC-4630-03 study will incorporate the following safety monitoring and risks mitigation strategies:

- Safety measures to minimize risks to subjects have been incorporated in the design of the study and eligibility criteria to specifically exclude subjects who may be at increased risk of specific toxicities
- Medications known to prolong QT are prohibited during study drug administration
- Guidance for investigators to follow institutional guidelines/standard of care with respect to implementation of prophylaxis for specific toxicities (eg, antibacterials for infections) to minimize risk to subjects
- The study will include a safety run-in period that will evaluate DLTs and clear a combination dose by the Dose Committee as guided by the mTPI-2 algorithm (see [Appendix 11](#))
- In addition to DLT criteria, dose modifications after the DLT window have been included in order to reduce the risk of toxicity while continuing to provide subjects a potential treatment opportunity
- Safety monitoring (consisting of AE assessments, physical examinations, vital signs measurements, electrocardiograms [ECGs], clinical laboratory tests, ECOG performance status [PS], and echocardiogram [ECHO]/multigated acquisition [MUGA] scans), will occur at regular intervals throughout the study
- As a precaution, subjects receiving strong CYP3A4 inhibitors (see [Appendix 8](#)) and/or inducers are excluded, until further data become available
- Invasive measures in this study are limited to venipuncture (all study subjects) and tumor biopsies in subjects, when feasible. The primary purpose of the pretreatment biopsies is to assess tumor biology and explore predictive biomarkers ([Hirsch, 2003](#)) (see [Section 8.7](#)).
- An Internal Safety Monitoring Committee (ISMC) will be used to monitor the safety of RMC-4630 and sotorasib combination therapy throughout the study. The ISMC is RMC-4630-program specific and will review emergent safety data at regular intervals for all subjects during the trial in conjunction with data from other active RMC-4630 clinical trials. Additional details are provided in [Section 8.3.6.2](#).

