16. Subject has any other unstable or clinically significant concurrent medical condition (including, but not limited to substance abuse, uncontrolled intercurrent illness such as active infection, arterial thrombosis, or symptomatic pulmonary embolism) that would, in the opinion of the investigator, jeopardize the safety of a subject, impact their expected survival through the end of the study participation, and/or impact their ability to comply with the protocol. Any subject who had a pulmonary embolism within 3 months of C1D1 will also be excluded.
17. Subject has had prior therapy with one or both of the following agents, meets criteria for exclusion:
 - a. *KRAS*^{G12C} inhibitor
 - b. SHP2 inhibitor
18. Subject has had treatment with chemotherapy or biologics/monoclonal antibodies < 21 days or 5 half-lives (whichever is shorter) before C1D1.
19. Subject has had treatment with non-thoracic radiation therapy < 14 days before C1D1.
20. Subject has had treatment with tyrosine kinase inhibitor (TKI), hormonal therapy (except megestrol acetate) < 7 days before C1D1.
21. Subject has had treatment with immunotherapy (eg, checkpoint inhibitors) 14 to 21 days before C1D1, depending on cycle length of drug.
22. Subject has had treatment with all other anticancer treatments including investigational agents that do not fit in the above categories < 21 days before C1D1.
23. Use of proton pump inhibitors (PPIs) within 3 days or H2 receptor antagonists (H2-blockers) within 1 day prior to study intervention. Subjects using an antacid or other acid reducing agent must have a 24-hour wash out period prior to initiation of study treatment.

24. Subject has had consumption of strong CYP3A4 inducers or inhibitors within 7 days prior to initiation of study treatment and requires treatment with strong CYP3A4 inducers or inhibitors.
25. Subject has had consumption of strong P-glycoprotein (P-gp) inhibitors (eg, cyclosporine, tacrolimus) within 7 days prior to initiation of study treatment and requires treatment with a strong P-gp inhibitor.
26. Use of known CYP3A4 and P-gp sensitive substrates (with a narrow therapeutic window), within 14 days or 5 half-lives of the drug prior to study day 1 that was not reviewed and approved by the principal investigator.
27. Subject has had clinically significant reversible toxicities from prior cancer therapy that have not recovered to Grade 1 or baseline, except for alopecia.

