5.3. Lifestyle Considerations

5.3.1. Meals and Dietary Restrictions

Subjects should refrain from consumption of grapefruit or grapefruit-containing products, or Seville oranges from 7 days before the start of study treatment until after the final dose.

Fasting (except water) 1 hour prior to and 1 hour after each RMC-4630 dose is required. Fasting is **NOT** required for sotorasib; however, on days when both medications are taken together, fasting is requisite due to the requirements of RMC-4630. Sotorasib tablets should be swallowed whole, with or without food.

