6.6. Prohibited Concomitant Therapy

In addition to prohibited medications/foods listed in the Exclusion Criteria ([Section 5.2](#)), a complete list of prohibited medications during study treatment is provided in [Appendix 8](#).

The following medications are prohibited while on study treatment:

- PPIs and H2-blockers
- Medications known to prolong QTc interval
- Anti-cancer therapy (except study treatment medications)
- Strong CYP3A4 inhibitors and inducers
- Strong P-gp inhibitors
- Known CYP3A4 and P-gp sensitive substrates (with a narrow therapeutic index), that were not reviewed and approved by the principal investigator

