8.3.1. Time Period and Frequency for Collecting AE and SAE Information

Monitoring and recording of AEs and SAEs will be conducted throughout the study. After the signing of the ICF, but prior to initiation of study treatment, only SAEs caused by a protocol-mandated treatment will be collected (eg, SAEs related to invasive procedures, such as biopsies or medication washout). Any medical occurrence that begins before the start of study treatment but after obtaining informed consent, and which is not considered an SAE caused by a protocol-mandated treatment, will be recorded on the Medical History/Current Medical Conditions Section of the eCRF rather than the AE section.

All AEs and SAEs will be collected from the start of treatment until 30 days after the last dose, or upon initiation of alternative cancer treatment, whichever occurs first. After this period, investigators should report only SAEs that are thought to be related to RMC-4630 and/or sotorasib.

Any SAE that is determined to be study-treatment related (possibly, probably, or definitely related) will be followed to resolution or stabilization, until it is determined to be irreversible by the investigator, the subject is lost to follow-up, or it has been determined that the study treatment is not the cause of the AE/SAE, whichever occurs first. After this period, investigators should report only SAEs that are thought to be related to RMC-4630 and/or sotorasib.

All SAEs will be recorded and reported to the Sponsor or designee within 24 hours of investigator awareness, as indicated in [Appendix 3](#). The investigator will submit any updated SAE data to the Sponsor within 24 hours of it being available. During the Extended-Use phase of the study, only SAEs (irrespective of causality) and related AEs will be reported in the EDC. All SAEs will also be reported on the SAE Report Form.

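### Exclusions 24 and 25 join recent use and continuing need with 'and', so their 7-day window never excludes anyone on its own

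*Protocol*

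**What the plan says.** Section 5.2 of the protocol excludes a subject who meets any one of its numbered criteria, and Section 5 does not permit waivers. Each criterion therefore has to work as printed.

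Exclusion 24 covers a subject who consumed a strong CYP3A4 inducer or inhibitor "within 7 days prior to initiation of study treatment and requires treatment with strong CYP3A4 inducers or inhibitors". Exclusion 25 covers a subject who consumed a strong P-gp inhibitor "within 7 days prior to initiation of study treatment and requires treatment with a strong P-gp inhibitor".

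Neighbouring criteria are built differently. Exclusion 23 reads "Use of proton pump inhibitors (PPIs) within 3 days or H2 receptor antagonists (H2-blockers) within 1 day prior to study intervention" and adds no second condition. Exclusions 18, 19, 20 and 22 also turn only on how recently the treatment was given. Section 5.3.1 asks subjects to avoid grapefruit products and "Seville oranges from 7 days before the start of study treatment until after the final dose", and Appendix 8 lists grapefruit juice as a strong CYP3A inhibitor.

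Three further sections bear on the same drugs. Section 2.2.2.1 states that "RMC-4630 remains a putative substrate of CYP3A4" and urges caution over giving the drugs together. Section 2.2.2.4 puts the precaution in terms of current users ("As a precaution, subjects receiving strong CYP3A4 inhibitors" and/or inducers are excluded). Section 6.6 opens its list with "The following medications are prohibited while on study treatment".

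**The concern.** A look-back tied to the start of treatment normally works as a washout: anyone exposed inside it waits or is excluded. Joined by 'and' to a continuing need, it cannot do that. It can only shrink the group that the need clause would exclude by itself. A subject who takes a strong CYP3A4 inhibitor up to the day before the first dose, and stops in order to qualify, meets the eligibility rules as far as Exclusion 24 is concerned.

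What is at stake is exposure in Cycle 1. If RMC-4630 is cleared by CYP3A4, residual inhibition or induction could shift its concentrations in the cycle that serves as the DLT window (Section 8.4) and provides the first PK samples (Section 8.6). Sponsor confirmation of enrolment (Section 6.3) would not stop this, because it reviews subjects against the criteria as written.

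**Working it through.** The defect is one of logic, so the check is a truth table followed by a search for any other rule that supplies the missing washout.

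**Step 1: the printed rule.** Let A = drug consumed within 7 days before first dose, and B = subject requires treatment with the drug.

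| A | B | Printed (A and B) | Amended (A or B) |
|---|---|---|---|
| yes | yes | excluded | excluded |
| yes | no (just stopped) | not excluded | excluded |
| no | yes | not excluded | excluded |
| no | no | not excluded | not excluded |

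The printed form excludes 1 of the 4 combinations and the amended form excludes 3. In the printed form A alone never excludes. The third row shows the opposite gap: a subject who needs the drug but last took it 8 days ago is not caught either, although Section 6.6 would bar its use once treatment starts.

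**Step 2: does another rule close the second row?**

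- Sections 2.2.2.1, 2.2.2.4 and 6.6 concern co-administration, subjects receiving the drug, and use during treatment. They do not contradict Exclusions 24 and 25, but none sets an interval for a drug already stopped.
- Exclusions 20 and 22 impose 7-day and 21-day limits on anticancer drugs. They would reach Appendix 8 entries such as lapatinib or enzalutamide, on the assumption that these are anticancer drugs; the documents do not class them.
- Exclusion 26 imposes 14 days or 5 half-lives, but only for sensitive substrates with a narrow therapeutic window, and the principal investigator can approve an exception.
- Section 5.3.1 covers grapefruit and Seville oranges only, and is an instruction to subjects, not an eligibility criterion.

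Clarithromycin, itraconazole, ketoconazole, rifampin, carbamazepine and phenytoin all appear in Appendix 8 as strong CYP3A inhibitors or inducers. None is on its sensitive-substrate lists. For a recently stopped course of any of these, no other washout rule applies.

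**Step 3: how far does the stated rationale reach?** The CYP3A4 statement in Section 2.2.2.1 supports Exclusion 24. For Exclusion 25 there is no counterpart: no section says that RMC-4630 or sotorasib is a P-gp substrate. Section 6.5 discusses P-gp only in terms of effects on other medicines that are substrates. The wording fault is the same in both criteria, but the documented consequence belongs to Exclusion 24.

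**The case against.** The strongest reply is that the authors meant to exclude continuing users only. Section 2.2.2.4 is the one place that states the aim of the CYP3A4 exclusion, and it speaks of subjects receiving these drugs. On that view the 7-day clause merely identifies current use. This is a possible reading, so the intended 'or' is an inference from Exclusion 23, Section 5.3.1 and the form of the neighbouring criteria. The literal effect is not an inference: under either intent a subject can stop the day before dosing and enter.

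It is also fair that long-term users who still need the drug are excluded, since both halves are met. Exclusion 2 (treated CNS disease must be asymptomatic without anticonvulsants) and Exclusion 16 (uncontrolled active infection) may keep out some people on the relevant drugs. These narrow the gap, but they are conditions of disease and not washouts.

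Three stronger readings are tempting and are not supported:

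- A reader might take Section 8.3.1, which mentions "SAEs related to invasive procedures, such as biopsies or medication washout", as proof that a washout of CYP3A4 and P-gp agents was planned. Exclusion 23 itself requires a 24-hour washout of antacids and other acid-reducing agents, which accounts for the phrase.
- A reader might count the uncovered entries in Appendix 8 and treat the count as the size of the problem. A list of drug names says nothing about how many subjects took one in the relevant week, and sorting the names requires drug classes that the documents do not give.
- A reader might infer that dose selection is compromised. In Appendix 11, with 6 evaluable subjects, 1 DLT means escalate and 2 means stay, so one event can matter. That is true of any single DLT. The run-in is about 6 to 12 subjects (SAP Section 2.3) and may be skipped, the table only guides the Dose Committee, and the expansion dose rests on the totality of data from two studies. No document gives the size or duration of any residual effect.

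**Conclusion.** Exclusions 24 and 25 are wrong as written, with small impact. The 7-day window has no independent force, and for several common strong CYP3A inhibitors and inducers nothing else in the protocol provides a pre-dose interval. This conclusion rests only on the printed wording.

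The importance of the gap rests on two assumptions: that RMC-4630 really is a CYP3A4 substrate, which the protocol calls only putative, and that some subjects stop such a drug within 7 days of starting. The second is probably uncommon and cannot be sized from the documents. The case is good for Exclusion 24. For Exclusion 25 it is one of consistency. No sample size, endpoint or analysis is affected.

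**What to change.** In Exclusion 24 replace 'and requires' with 'or requires'. Make the same change in Exclusion 25 so that the two criteria match.

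No new data are needed, because Table 1 footnote 18 already records concomitant medications from 7 days before Cycle 1 Day 1. The cost falls on subjects who stop late. If the last dose is d days before the planned start, and a 7-day gap is accepted as clear, the added wait is 7 − d days: 6 days for d = 1, and at most 7 for d = 0. With a 6-day delay, a test under the 14-day screening window that was done more than 14 − 6 = 8 days before the planned start would have to be repeated. Section 5.4 allows rescreening only within 5 days of a screen failure, which is shorter than this wait. Such a subject is therefore better held in screening than recorded as a screen failure, or the rescreening limit could be relaxed for this reason.

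The documents do not say whether enrolment has closed. If it has, the useful step is to use the prior-medication listing in SAP Section 7.4.5 to identify anyone who took a strong CYP3A4 agent in the week before the first dose, and to note those subjects when Cycle 1 PK and DLT data are reviewed.

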5.3. Lifestyle Considerations

5.3.1. Meals and Dietary Restrictions

Subjects should refrain from consumption of grapefruit or grapefruit-containing products, or Seville oranges from 7 days before the start of study treatment until after the final dose.

Fasting (except water) 1 hour prior to and 1 hour after each RMC-4630 dose is required. Fasting is **NOT** required for sotorasib; however, on days when both medications are taken together, fasting is requisite due to the requirements of RMC-4630. Sotorasib tablets should be swallowed whole, with or without food.

5.4. Screen Failures

Screen failures are defined as subjects who consent to participate in the clinical study but are not subsequently able to receive treatment in the study. A minimal set of screen failure information is required to ensure transparent reporting of screen failure subjects to meet the Consolidated Standards of Reporting Trials (CONSORT) publishing requirements and to respond to queries from regulatory authorities. Minimal information includes demography, screen failure details, eligibility criteria, and any serious adverse event (SAE).

Individuals who do not meet the criteria for participation in this study (ie, screen failure) may be rescreened within 5 days of the initial screening date of screen failure. Rescreened subjects should be assigned the same subject number as for the initial screening. Only hematology, chemistry, and coagulation tests may need to be repeated if outside the screening window. Other clinical testing will not need to be repeated if outside screening window (ie, within 5 days).

